**Research Hypothesis:**

BMS-931699 (Lulizumab) will have greater clinical efficacy compared to placebo on the British Isles Lupus Assessment Group (BILAG)-based Composite Lupus Assessment (BICLA) score, when added to stable background standard of care in subjects with active manifestations of systemic lupus erythematosus (SLE) including, at a minimum, elevated antinuclear antibodies, arthritis, and/or cutaneous manifestations satisfying the BILAG “A” or “B” criteria.

## **Schedule of Analyses:**

The following analyses will be performed:

- An interim analysis for the safety/RO at Day 29 of Part 1 when at least 6 patients per treatment arm have either reached Study Day 29 or discontinued (refer to the details in [Section 7.5.5](#));
- An interim analysis for futility and dose adaptation will be performed when approximately 30 patients per treatment arm (including the patients from part 1) have completed at least 84 days of treatment period or discontinued the treatment;
- A final analysis will be performed after the last treated subject in the study reaches the end of the short-term period.

## **2 STUDY DESCRIPTION**

### **2.1 Study Design**

This is a Phase 2, parallel-arm, randomized, double-blinded, multicenter, international study, with an adaptive design.

The study will comprise a short-term period (Part 1 and Part 2), and a long-term extension (LTE) period. This SAP covers the short-term period of the study.

**Part 1** of the short-term period will focus on assessing safety and RO and will be limited to a maximum of 50 patients (approximately 6-10 patients/arm) who will be included in the Safety/RO interim analysis (IA). These patients will continue study treatment beyond the IA for Safety/RO and be treated for up to 24 weeks and be followed for 6 additional weeks after treatment is completed. Treatment could be shorter if IA for Safety/RO analysis indicates one or more arms should be dropped.

**Part 2** of the short-term period will start once cumulative safety profile is considered acceptable and RO data for 6-10 subjects per cohort dosed for >28 days is available and the interim analysis from Part 1 is completed. Approximately 300 subjects will be randomized into this part of the study (number of patient to be randomized into Part 2 may increase based on the results of the futility interim analysis).

All subjects will undergo screening evaluations to determine eligibility and allow down titration of prednisone (or prednisone equivalent) prior to administration of study medication. The screening period will have a duration of approximately 28 days (+/- 2 days). All eligibility criteria must be met prior to Day 1. In the event of technical difficulties leading inconclusive assessments that would go beyond the allowed window, the study medical monitor must be consulted prior to conducting Day 1. On Day 1, eligibility of subjects will be confirmed and eligible subjects will receive their first dose of study medication.

Dose may be adapted based on results of the planned interim analyses from Part 1 and Part 2, as follows:

- Safety and RO interim analysis: safety and RO analysis will be performed when approximately 6 to 10 subjects per arm have reached Study Day 29. Based on the results of this analysis, dose arm(s) may be adjusted or may be dropped.
- Interim analysis for futility and dose adaptation on BICLA response, SRI response, ACR28 and some SLE biomarkers (such as auto-antibodies, complement levels, etc.) with possible exploratory exposure response analysis, will be performed when approximately 30 subjects per arm have reached Study Day 85 (12 weeks), including subjects from Part 1 and Part 2, of treatment or have discontinued prior to reaching study Day 85). Analysis will be performed by an unblinded Sponsor team, while maintaining blind at the site and subject level. Based on the results, the dose levels and sample size may be modified.
- Ongoing assessment of safety will be performed by an independent Data Monitoring Committee (DMC) and an internal unblinded safety monitoring team. Both entities may make recommendations to the Sponsor regarding conduct of study and dose adjustment based on safety observations.

Following interim analyses and DMC reviews, dose arm(s) may be modified based on the results, as follows:

- If one or more arms are added, future randomizations will include the new arm(s).
- If one or more arms are dropped for safety reasons, randomization into that arm will be terminated and all subjects currently randomized to that or those arm(s) will be discontinued from receiving study medication.
- If one or more arms are dropped due to inadequate RO, there will be no new randomizations into that dose arm; subjects currently randomized may continue at the Investigator discretion.

The **long-term extension (LTE) period** is optional and will include eligible subjects who have completed Day 169 (week 24) of treatment and consent to participate. This period of the study will remain blinded but will no longer have a placebo arm. Eligible subjects will remain on their originally-assigned dose arm, unless they were on the placebo arm during the short-term period. Placebo-arm subjects will be re-randomized into one of the existing active arms at Day 169 (24 weeks). Re-randomization of the placebo subjects will be done by IVRS and only the unblinded pharmacist/drug preparer will know the new randomization arm. The LTE will remain blinded to the study team and study personnel.

[figure not shown]
The long-term extension period will not have interim analyses for dose adaptation. However, the BMS unblinded safety committee will continue to review the safety data and discuss it with the DMC (also unblinded), as needed. During their evaluation of adverse events, if a significant safety concern is identified, these two committees may propose that one or more dose arms are

dropped. If one or more dose arms are dropped for safety reasons, all subjects currently receiving that or those dose(s) will be discontinued from receiving study medication.

[figure not shown]
A separate document (LTE SAP) describes the analysis plan for the long-term extension period.

The study design schematics are presented in Figure 2.1-1, [Figure 2.1-2](#), [Figure 2.1-3](#), and [Figure 2.1-4](#) below.

[figure not shown]
### Figure 2.1-1: Overall Study Design

[figure not shown]
**Figure 2.1-2:** Study Design Schematic - Part 1

**Figure 2.1-3:** Study Design Schematic - Part 2

**Figure 2.1-4: Long-Term Extension Schematic**

\* Treatment arm may or may not be included based on Interim Analyses.

⊗ Subjects in the placebo arm will be re-randomized to existing active treatment arms at Day 169.

# FU Day 42 to occur after last dose of study medication, whether last dose is in short term or long term periods.

Physical examinations, vital sign measurements, 12-lead electrocardiograms (ECG), and clinical laboratory evaluations will be performed at selected times throughout the study. Subjects will be closely monitored for adverse events throughout the study. Blood will be collected for pharmacokinetic (PK) and pharmacodynamic measurements as well as for safety monitoring.

The approximate duration of the short-term period (Parts 1 and 2) of the study is 238 days (34 weeks), including: 28 days (4 weeks) of screening, 168 days (24 weeks) of treatment, and 42 days (6 weeks) of safety follow-up. If subject is eligible and opts to continue into LTE, the 42-day follow-up visit will not be performed after the short-term period is completed and subject will enter LTE directly. If subject opts not to enter LTE then a follow-up visit will be completed 42 days after end of treatment. At the time of writing there is no defined end date to the long-term extension period, however, the LTE provision may be further adjusted based on results from the ongoing lulizumab development program. Subjects discontinuing treatment during the LTE period will complete the follow-up visit approximately 6 weeks after receiving their last dose of study medication.

Subjects randomized in the short-term period (either Part 1 or Part 2) will be treated for up to 24 weeks, will have the same procedures performed and will follow the same visit schedule. All subjects will account for the approximately 350 subjects planned to be randomized in this study.

Approximately 125 sites will participate in this study, which will be conducted globally and should include, but will not be limited to, participation of countries located in North America and Europe.

Subjects who discontinue from the study will have one follow-up visit, approximately 42 days (6 weeks) after receiving their last dose of study medication, to perform safety assessments. During this period, when subjects are no longer receiving study drug, it is recommended that they are not treated with other biologic therapy, due to the compound's half-life. However, this decision remains at the investigator's discretion. If the study drug becomes commercially available, and if the subject chooses to receive treatment with the commercial product, then the subsequent post-dose follow-up visits are not required.

For more details, refer to the study protocol.

## **2.2 Treatment Assignment**

After completion of all screening evaluations and confirmation of eligibility, subjects will be randomized on Day 1 to one of the following dosing arms in a 1:1:1:1:1 ratio in Part 1 of the study design: BMS-931699 at 12.5mg weekly sub-cutaneous (SC) injection, BMS-931699 at 12.5mg every other week (EOW) SC injection, BMS-931699 at 5mg EOW SC injection, BMS-931699 at 1.25mg EOW SC injection, or Placebo SC injection. The randomization ratio and the treatment arms may be modified based on the results from the two interim analyses defined in [Section 7.6](#).

In this study, subjects will be randomized to receive one of the treatments according to a computer-generated randomization scheme prepared by a Randomization Coordinator within the Drug Supply Management Department of BMS Research and Development.

During the Screening visit, the investigative site will call into the enrollment option of the Interactive Voice Response System (IVRS) designated by BMS for assignment of a 5-digit subject number that will be unique across all sites. Enrolled subjects, including those not dosed, will be assigned sequential subject numbers starting with 00001, 00002, 00003.... 00010. The patient identification number (PID) will ultimately be comprised of the site number and subject number. For example, the first subject screened (i.e., enrolled) at site number 1, will have a PID of 0001 00001. Once it is determined that the subject meets the eligibility criteria following the Screening visit, the investigative site will call the IVRS to randomize the subject into the treatment period.

Every randomized subject will be required to come to the clinic/research center weekly to be dosed. This will ensure double-blind is maintained despite the variability of regimens. Subjects randomized to weekly subcutaneous injections of either placebo or BMS-931699 will be dosed weekly as per schedule and subjects randomized to one of the every other week arm will be alternating between receiving a subcutaneous injection of BMS-931699 one week and one of placebo the following week.

## **2.3 Blinding and Unblinding**

### **2.3.1 *Blinding at the Study Sites***

The subjects and clinical assessor(s) will not be aware of which treatment is being administered to the subjects enrolled in the study. The pharmacist (or qualified drug preparation person) will be unblinded to study medication (BMS-931699 or placebo).

The pharmacist (or qualified drug preparation person) will know the randomization assignments and prepare the appropriate dose of active BMS-931699 or placebo accordingly. The prepared drug must be supplied to study personnel in a manner such that neither study personnel nor subjects will be aware of whether they receive active drug or placebo.

### **2.3.2 *Unblinding of the Study Sites***

Blinding of treatment assignment is critical to the integrity of this clinical study. However, in the event of a medical emergency or pregnancy in an individual subject in which knowledge of the investigational product is critical to the subject's management, the blind for that subject may be broken by the investigator. The subject's safety takes priority over any other considerations in determining if a treatment assignment should be unblinded.

Before breaking the blind of an individual subject's treatment, the investigator should determine that the unblinded information is necessary, i.e., that it will alter the subject's immediate management. In many cases, particularly when the emergency is clearly not related to the investigational product, the problem may be properly managed by assuming that the subject is receiving active product. It is highly desirable that the decision to unblind treatment assignment be discussed with the Medical Monitor, but the investigatory always has ultimate authority for the decision to unblind. The Principal Investigator should only call in for emergency unblinding AFTER the decision to discontinue the subject has been made.

For this study, the method of unblinding for emergency purposes is IVRS.

For information on how to unblind in an emergency, consult the IVRS manual.

In cases of accidental unblinding, contact the Medical Monitor and ensure every attempt is made to preserve the blind.

Any request to unblind a subject for non-emergency purposes should be discussed with the Medical Monitor.

[figure not shown]
In case of an emergency, the Investigator(s) has unrestricted access to randomization information via the Interactive Voice Response System (IVRS) and is capable of breaking the blind through the IVRS system without prior approval from sponsor. Following the unblinding the Investigator shall notify the Medical Monitor and/or Study Director.

### **2.3.3 *Other Unblinding Information***

For analysis of pharmacokinetic and anti-BMS-931699 samples, the Bioanalytical Sciences Group at BMS, and/or the designated vendor performing the analysis will be unblinded to the randomized treatment assignments in order to minimize unnecessary analysis of samples from control group subjects.

In collaboration with the DMC, an unblinded internal safety monitoring team, which is independent of the study team, will review the safety data throughout the study and will provide recommendations to the blinded study team. Therefore, the unblinded internal safety monitoring team can be unblinded. The unblinded internal safety monitoring team will have members from the Global Pharmacovigilance and Epidemiology group (GPV&E) within BMS.

The following BMS personnel will form the unblinded team (Independent of the blinded study team): one or more GPV&E physicians, one or more PK scientists, pharmacometrics analysts, one or more statisticians and programmers.

## 2.4 Protocol Amendments

**Table 2.4-1: Protocol Amendments**

Amendment No.	Amendment Date	Main Purpose of Amendment
1	20-AUG-2014	Pharmacogenetics amendment
2	24-SEP-2014	Brazil specific amendment
3	16-DEC-2014	Japan specific amendment
4	11-FEB-2015	Argentina specific amendment
5	16-MAR-2015	Japan specific amendment to add Exclusion Criteria regarding Laboratory Test of Hepatitis-B and Allergies
6	28-APR-2015	Revised Protocol no.1 (adding LTE, allowing MMF, edits, adding clarity)
7	29-JUN-2015	Canada specific amendment to limit LTE to 1yr (until further data are available)
8	01-Oct-15	Removing RNA testing (Site 152 (Japan) only)
9	22-Apr-16	To add intensive PK blood sample collections and also add sparse receptor occupancy samples in the PK substudy

### **3            OBJECTIVES**

#### **3.1        Primary Objective**

To compare the proportion of patients who achieve BICLA response (BICLA response rate) at Day 169 following 24-week treatment with BMS-931699 or placebo administered on a stable background therapy.

#### **3.2        Secondary Objectives**

To assess:

- The safety and tolerability of treatment with BMS-931699 in patients with active SLE
- The proportion of patients who meet response criteria for the SLE Responder Index (4) [SRI (4)], SRI(5), and SRI(6)] at Day 169 following 24-week treatment with BMS-931699 or placebo administered on a stable background therapy.
- The proportion of patients with SLE Responder Index [SRI(4), SRI(5), and SRI(6)] at Day 85 following 12-week treatment with BMS-931699 or placebo administered on a stable background therapy.
- The proportion of patients with a BICLA response at Day 85 following 12-week treatment with BMS-931699 or placebo administered on a stable background therapy.
- The improvement in the extent of cutaneous and mucous membrane activity, as measured by the Cutaneous Lupus Erythematosus Disease Area and Severity Index (CLASI) at Day 85 and Day 169
- Joint pain, tenderness and swellings as measured by the by American College of Rheumatology (ACR)28 at Day 85 and Day 169
- The other indices of SLE activity measured at Days 29, 57, 85, 113, 141, and 169 including:
  - ◆ The change from baseline in overall BILAG-2004 score. A major response is defined as described in Yee et. al. 2010 (A=12; B=8; C=1; D/E=0).
  - ◆ The change in overall Systemic Lupus Erythematosus Disease Activity Index 2K score (SLEDAI 2K)
  - ◆ The change from baseline in Physician's Global Assessment of disease activity (MDGA) score
- The systemic exposure of BMS-931699 in patients with SLE
- The cumulative corticosteroids use and immunosuppressant use over time
- The immunogenicity of BMS-931699
- Serum biomarkers C3, C4, anti-double-stranded deoxyribonucleic acid (anti-dsDNA), anti-nuclear antibody (ANA) and other autoantibodies at Day 85 and Day 169

- The pharmacodynamics (PD) of BMS-931699, including assessments potentially associated with target engagement (including receptor occupancy [RO]).

## 4 ENDPOINTS

### 4.1 Primary Efficacy Endpoint(s)

The primary efficacy endpoint is the proportion of subjects who achieve BICLA response at Day 169.

### 4.2 Secondary Efficacy Endpoint(s)

- Proportion of subjects who meet response criteria for the SLE Responder Index(4) [SRI(4)], SRI(5), SRI(6), and SRI(8) at Day 169
- Proportion of subjects who meet response criteria for the SLE Responder Index(4) [SRI(4)], SRI(5), SRI(6), and SRI(8) at Day 85
- Proportion of subjects with BICLA response at Day 85
- Change from baseline in CLASI score at Day 85 and Day 169

- Percentage of subjects with an improvement of at least 4 or an improvement of at least 50% from baseline in their CLASI score at Day 85 and Day 169
- Proportion of subjects with an improvement of at least 4 or an improvement of at least 20% from baseline in their CLASI score at Day 85 and Day 169
- Change from baseline in arthritis, as assessed by American College of Rheumatology (ACR) 28 joint counts of tender, swollen, and as well as active joints, i.e. those that are both tender and swollen at Day 85 and at Day 169
- The change from baseline in the following other indices SLE activity over time:
  - ◆ The overall BILAG-2004 score
  - ◆ The overall SLEDAI-2K score
  - ◆ The overall MDGA (Physician's Global Assessment of Disease Activity) score
- Change from baseline in SLICC/ACR Damage Index
- The cumulative corticosteroid and immunosuppressant use over time

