3.3.1 Inclusion Criteria

1. Signed Written Informed Consent

- a) Subjects must be willing to participate in the study and sign the informed consent.
- b) Subjects must be willing and able to complete all study specified procedures and visits.

2. Target Population

- a) Subjects must have SLE as defined by meeting 4 of the 11 classification criteria of the American College of Rheumatology for the classification of SLE, either sequentially or coincident. The 4 criteria need not be present at study entry, but have occurred at some time during the course of the disease and be documented.

b) Subject Re-screening: This study permits the re-screening of a subject that has discontinued the study as a pre-treatment failure (ie, subject has not been randomized / has not been treated). If re-screened, the subject must be re-consented.

Note (1): If a subject is being considered for re-screening, a full screening visit must be performed again.

Note (2): A subject can only be re-screened once (eg, if re-screening for the same subject fails, no additional re-screening is allowed).

c) At screening:

i) Subjects must have elevated ANA $\geq 1:80$ via immunofluorescent assay at the central laboratory or anti-dsDNA or anti-Sm above the normal level as determined by the central laboratory.

Note: For inclusion criterion 2c-i: If central laboratory results are negative and positive results are documented at the site, a single repeat of the central laboratory values is allowed. If the central laboratory repeat is negative, the patient is not eligible to be randomized.

ii) Subjects must have a SLEDAI ≥ 6 to be eligible. At least 4 of the points must be attributable to clinical criteria including at least one of the following clinical parameters: arthritis, rash, myositis, mucosal ulcers, pleurisy, pericarditis, vasculitis and excluding points from lupus headache and organic brain syndrome. Must be confirmed by the External Adjudication Committee.

Note: On Day 1, the SLEDAI 2K must be ≥ 4 including points from at least one of the following clinical components: arthritis, rash, myositis, mucosal ulcers, pleurisy, pericarditis, vasculitis, and fever and excluding parameters which require central laboratory results (hematuria, pyuria, urinary casts, proteinuria, positive anti-dsDNA, decreased complement, thrombocytopenia and leukopenia). Points from lupus headache and organic brain syndrome are excluded.

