iii) Subjects must have at least one of the following manifestations of SLE, as defined by the BILAG criteria as modified for use in this study, which must be confirmed by the External Adjudication Committee:

(1) BILAG A or B score in the Mucocutaneous body system

(2) BILAG A or B score in the Musculoskeletal body system due to active polyarthritis defined as follows:

(a) “BILAG A”: severe arthritis (BILAG #41) manifested by observed active synovitis in ≥ 2 joints with marked loss of functional range of movements and significant impairment of basic activities of daily living, that has been present on several days cumulatively over the past 4 weeks, including at the time of the screening visit. Basic ADLs are defined as the following activities which require assistance or assistive devices (at least one must be present and documented in source): ambulation, toileting, grooming including bathing, dressing, feeding oneself (not responsive to steroids up to 10 mg/day, antimalarials, NSAIDs).

(b) “BILAG B”: Moderate arthritis or tendonitis or tenosynovitis (BILAG #42) defined as tendonitis/tenosynovitis or active synovitis in ≥ 1 joint (observed or through history) with some loss of functional range of movements which lead to some loss of functional range of motion as manifested by effects on instrumental ADLs (such as cooking, driving, using the telephone or computer, shopping, cleaning, etc.) which has been present on several days over the last 4 weeks and is present at the time of the screening visit.

(3) if only one “B” and no “A” score is present in the Mucocutaneous body system or in the Musculoskeletal body system due to arthritis, then at least one B must be present in the other body systems for a total of 2 “B” BILAG body system scores.

iv) Unless intolerant, subjects must be currently receiving at least one of the following steroid-sparing agents for a minimum of 12 weeks, and at stable dose for at least 8 weeks (56 days) prior to signing consent:

Azathioprine (AZA), chloroquine, hydroxychloroquine, methotrexate (MTX), leflunomide, mycophenolate mofetil/mycophenolic acid*. Subjects must remain on stable dose throughout the study[#].

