### **8.1.2      *Evaluation of SRI(X)***

In addition to BICLA, a novel endpoint, the SLE Responder Index [SRI] with a modification used as a primary endpoint in the Anifrolumab study, the results of which were presented and published as an abstract at the American College of Rheumatology (ACR) National Meeting in November, 2015. The basic difference between the SRI defined in our protocol and the SRI in the Anifrolumab study is the addition of a fourth component of the endpoint. The original definition of SRI in the protocol does not include the fourth component based on the use of restricted medications.

The use of restricted medications is an important confounding factor when we analyze the endpoints such as BICLA, and SRI(X). Hence an additional component based on the use of restricted medications (same as the 4th component in the definition of BICLA) is deemed necessary to incorporate into the original definition of SRI (X) in the protocol. The modification to the existing definition of SRI is described below.

An SRI(X) [X= 4, 5, 6, and 8] response @ Day T (e.g. T = 85, 169) is defined as:

- a reduction in Day 1 SLEDAI-2K disease activity score of  $\geq X$  points at Day T; and,
- no worsening of disease (defined as an increase of  $\geq 10$ mm on a 100mm VAS from Day 1 as measured by the MDGA up to time T; and,
- no new BILAG-2004 Index 'A' organ system score and no more than one new or worsening BILAG-2004 Index 'B' organ system scores up to time T ; and,
- *No changes in concomitant medications according to the following criteria:*
  - No increase of or addition of a new immunosuppressant agent (azathioprine, methotrexate, anti-malarial) over baseline levels
  - No increase in corticosteroid dose above baseline level outside of those allowed per protocol.

If a subject failed any of the above criteria, the SRI(X) response status of the subjects will be set to non-responder.

For the determination of missing SRI(X) response status, all subjects who prematurely discontinue from the study medication will be imputed as a non-responder at all scheduled efficacy visits subsequent to the point of discontinuation.

If any subject has at most one missing component (e.g. MDGA for SRI(X)) at a given efficacy visit not due to premature discontinuation, the component-wise response status will be imputed based on the following rules.

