### **8.3 Missing Measurements**

For listings of binary response efficacy variables, missing values will be presented as missing. For determination of binary response variables, handling of missing values for BICLA and SRI(X) responses is addressed in [Sections 8.1.1](#) and [8.1.2](#) unless otherwise specified.

If the response cannot be assessed due to missing data or a subject's early discontinuation, the following conventions will be implemented in a sequence:

- Any subject who prematurely discontinues the trial during the Short-term period after receiving study medication will have data imputed as non-responder at all scheduled protocol visits subsequent to the point of discontinuation up to the end of the Short-term period.
- After any imputation above or none, if for some reason the binary variable still cannot be determined, including the case where baseline data is missing, then its value will be set to non-responder.

For the analysis of continuous efficacy variables, mixed model will be used based on assumption of data being missing at random. Subjects with only baseline observations will be excluded from any changes from baseline analyses.

For safety, PK and immunogenicity measures and biomarkers, missing values will not be imputed.

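### SRI(8), CLASI response and, perhaps negligibly, SRI(5) and SRI(6) count subjects who cannot respond from their Day 1 score, and no analysis of those able to respond is prespecified

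*SAP*

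**What the plan says.** **Entry.** Protocol 3.3.1 sets the screening floor: "Subjects must have a SLEDAI ≥ 6 to be eligible". The Day 1 floor is lower: "On Day 1, the SLEDAI 2K must be ≥ 4 including points from at least one of the following clinical components", counted while "excluding parameters which require central laboratory results". The same section admits a subject on a "BILAG A or B score in the Musculoskeletal body system due to active polyarthritis". An A score there suffices, or a B with a second B in another system, so skin disease is not required.

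**Response.** Beyond SRI(4), SAP 4.2 lists "SRI(5), SRI(6), and SRI(8) at Day 169", and the same thresholds at Day 85. SAP 8.1.2 defines SRI(X), for X = 4, 5, 6 and 8, with "a reduction in Day 1 SLEDAI-2K disease activity score of" at least X as its first component. Failing any component makes the subject a non-responder. SAP 4.2 defines CLASI response as an improvement of at least 4 points or at least 50% (a second version uses 20%), with no minimum Day 1 CLASI.

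**Analysis.** SAP 7.5 uses the Efficacy Analysis Population, which SAP 6.3 defines without reference to baseline activity. SAP 7.5.2 reports differences in proportions with 90% confidence intervals and no p-values. SAP 7.5.3 predefines one subgroup, Non-Japan, and leaves any others post hoc. SAP 8.3 has a catch-all: "if for some reason the binary variable still cannot be determined", the subject counts as a non-responder.

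**The concern.** A subject whose Day 1 SLEDAI-2K is below X cannot fall by X, whatever the treatment. A subject with a Day 1 CLASI of 0 cannot improve by 4 points, and has no defined percentage improvement. These subjects add to the denominator in every arm and to the numerator in none, so on the risk-difference scale they pull a real effect towards zero.

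The share affected can only stay level or rise with X. A decline in the treatment difference from SRI(4) to SRI(8) would therefore mix the drug's effect with the distribution of Day 1 scores, and no planned SRI(X) or CLASI-response table separates the two. SRI(8) is the most exposed. It was added in the SAP (Protocol 8.3.2.1 stops at SRI(6)) and has the widest range of Day 1 scores that rule out response. SRI(6) also matters because SAP 7.5.3 to 7.5.5 carry it into the subgroup, sensitivity and per-protocol analyses.

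**Working it through.** **1. Who cannot respond**

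| Endpoint | Day 1 value that rules out response | Needs a fall below the screening floor of 6? |
|---|---|---|
| SRI(4) | none at or above the Day 1 floor | – |
| SRI(5) | 4 | yes |
| SRI(6) | 4 or 5 | yes |
| SRI(8) | 4 to 7 | no, 6 and 7 already qualify |
| CLASI response | 0 only; 1 to 3 can still qualify by percentage | not applicable |

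The Day 1 floor of 4 is a count without central-laboratory items, whereas SRI(X) uses the SLEDAI-2K score without that exclusion. A Day 1 total of 4 is therefore possible only with no laboratory points.

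**2. The plan's own figures**

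The documents give no rates or power for SRI(X) or CLASI response. The only planning rates are for BICLA (Protocol 8.1, SAP 5): 70 per arm, one-sided 0.05, continuity-corrected, 25% on placebo, with at least 89% power at 50% and 74% at 45%. Both reproduce closely. The effective sample size is 70 × (1 − 1/(70d))², where d is the difference:

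- d = 0.25: 62.2 per arm, power 90.0% (exact enumeration 89.8%).
- d = 0.20: 60.4 per arm, power 75.0% (exact enumeration 74.7%).

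**3. Dilution**

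Let a share q of each arm be unable to respond, with rates rT (active) and rP (placebo) among the rest. Then:

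- expected all-subject difference = (1 − q)·rT − (1 − q)·rP = (1 − q)(rT − rP)
- risk ratio = (1 − q)rT / ((1 − q)rP) = rT/rP, unchanged
- if rT = rP, the difference is zero with or without dilution.

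Assumption: BICLA planning rates of 45% and 25% among those able to respond, 70 per arm. The 90% half-width is 1.645 × √(pT(1 − pT)/n + pP(1 − pP)/n).

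| q | All-subject difference ± half-width (n = 70) | Able-to-respond difference ± half-width | n per arm, restricted |
|---|---|---|---|
| 0 | 20 ± 13.0 points | 20 ± 13.0 points | 70 |
| 10% | 18 ± 12.7 | 20 ± 13.7 | 63 |
| 20% | 16 ± 12.3 | 20 ± 14.5 | 56 |
| 30% | 14 ± 11.8 | 20 ± 15.5 | 49 |
| 40% | 12 ± 11.2 | 20 ± 16.7 | 42 |

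At q = 30%, all subjects: rates 0.315 and 0.175; √(0.315 × 0.685/70 + 0.175 × 0.825/70) = 0.0717; × 1.645 = 0.118. Restricted: √(0.45 × 0.55/49 + 0.25 × 0.75/49) = 0.0942; × 1.645 = 0.155.

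At 50% against 25%, the all-subject difference is 22.5, 20.0, 17.5 and 15.0 points at the same values of q, instead of 25.

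**4. Single trials**

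The shrinkage holds in expectation. In 200,000 simulated trials at 50% against 25%, the all-subject difference was at least as large in absolute size as the restricted one in about 12% of trials at q = 10% and about 6% at q = 20%, through chance imbalance in q.

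**The case against.** The strongest reply is that this is a choice of estimand. Protocol 8.3.2.1 defines these endpoints as proportions of subjects, and the all-subject difference is a valid randomised estimate for the enrolled population. That stands, and it is why the planned analysis should not be demoted.

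Four other points stand in whole or in part.

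- **SRI(5) and SRI(6).** A reader might infer that they suffer as SRI(8) does. The documents do not support that. A blocked subject must have dropped from at least 6 at screening to 4 or 5 on Day 1. Screening lasts about 28 days (Protocol 3.1) and the index uses a 30-day window (Protocol 5.4.1.1), so many screening manifestations may still count. The Day 1 rule permits such subjects, but their share could be near zero.
- **Comparability across thresholds.** A reader might infer that the planned SRI differences cannot be compared with one another. They share one denominator, and every SRI(8) responder is also an SRI(4) responder. It is the restricted versions that use a different population for each X.
- **Precision.** Restricting raises the ratio of estimate to standard error only slightly (2.12 against 1.95 at q = 30% in the table above), and no test is planned. On the planned output the interval gets wider. The gain is in interpreting the estimate.
- **CLASI of 0.** A reader might take SAP 8.3 to say that such a subject is a non-responder. Its catch-all is introduced for missing data and early discontinuation, and a measured 0 is neither. Non-response is the likely result, but the SAP does not state it.

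The mixed-model analyses of SLEDAI-2K and CLASI change, and SRI(4), recover part of the information. They do not give an undiluted response rate at the higher thresholds.

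**Conclusion.** The point holds as a cheap improvement to secondary endpoints. The entry floors, response definitions and denominator together admit subjects who cannot respond. This is clearest for SRI(8) and, subject to the inference about a score of 0, for CLASI response. It is possible but perhaps negligible for SRI(5) and SRI(6). Expected differences in proportions are multiplied by (1 − q).

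The size rests on two assumptions: q, which the documents do not give, and response rates borrowed from BICLA. Over q = 10 to 40%, a 20-point effect would be expected to show as 18 down to 12 points.

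A reader might infer that every treatment difference in the trial is shrunk, or that the planned analysis is biased. Neither follows. The effect is in expectation, on the risk-difference scale, when a true effect exists, and only for the named endpoints. BICLA, SRI(4) and the continuous endpoints are unaffected.

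**What to change.** In SAP 4.2 and 7.5.2:

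- Keep the protocol-defined all-subject SRI(X) analysis as planned.
- Prespecify alongside it SRI(5), SRI(6) and SRI(8) in subjects whose Day 1 SLEDAI-2K is at least X.
- Analyse CLASI response in subjects with a Day 1 CLASI above 0, and state explicitly how a Day 1 CLASI of 0 is classified in the all-subject version.
- Report the number excluded per arm for each restricted analysis, so that q is visible.

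Both restrictions use values measured before dosing, so the randomised comparison is preserved, and no new data are needed. Fixing them before unblinding avoids a post hoc choice.

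The cost is SAP wording, duplicate tables, smaller denominators and wider 90% intervals (half-width 0.155 against 0.118 at q = 30% in the illustration). The restricted SRI(X) results would also come from a different population at each X, and the tables should say so.
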